7.1.1 Screening

Written informed consent must be obtained before any study specific procedure is performed. Screening assessments to confirm eligibility into the main study should be performed as per the schedule of assessments. Re-screening of patients will not be allowed, but laboratory parameters which do not meet the inclusion criteria may be re-tested within the screening window (Day -28 to Day -1).

7.1.1.1 Eligibility screening

After the patient has signed the consent form to participate in the study, a registration sheet will be completed and faxed or emailed to the Novartis for approval and acknowledgement of entry of the patient onto the study. Details on the enrollment process are provided to investigators as the instruction.

7.1.1.2 Information to be collected on screening failures

Patients who sign an informed consent but fail to be started on treatment for any reason will be considered a screening failure.

The following eCRFs must be completed for screening failure patients:

- Screening Phase Disposition page (including reason for not being started on treatment)
- Informed consent
- Demography
- Adverse Events (only if an SAE occurs)
- Inclusion/Exclusion criteria
- Death
- Withdrawal of consent

7.1.1.3 Patient demographics and other baseline characteristics

Data to be collected on patient characteristics at screening include:

- Demography (including: date of birth, age, patient initials, gender, childbearing potential, race and ethnicity, or as allowed by local regulations)
- Relevant medical history
- History of smoking
- NSCLC diagnosis and extent of disease, including:
 - Date of diagnosis of NSCLC
 - ALK status documentation using the Vysis ALK break-apart FISH assay. If such documentation is not available, ALK status must be confirmed using the Vysis ALK break-apart FISH test in site locally (preferably using a new tumor biopsy obtained prior to the first LDK378 dose or, if not available, in archival tumor obtained at or since the time of diagnosis) prior to study entry.
 - Site of active disease
 - Characteristics of disease

- Concomitant molecular alteration when available (and results of all the tests performed even if wild type)
- Prior antineoplastic therapies (medications, radiation, surgeries)
- Prior and Concomitant Medications, surgical and medical procedures
- Neurological examination and use of steroids to control CNS symptoms (only for patients with symptomatic CNS metastases)

All other medications taken within 28 days before the first dose of study treatment is administered must be recorded on the Prior and Concomitant medication eCRF page and updated on a continual basis if there is new change to the medication.

7.1.2 Treatment period

The study treatment phase begins on Cycle 1, Day 1 with the first administration of LDK378 and will continue until unacceptable toxicity that precludes further treatment, start of a new anti-cancer therapy, treatment is discontinued at the discretion of the investigator and/or patient death. If a patient experiences disease progression (radiologically documented according to RECIST 1.1 as assessed by the investigator), LDK378 administration may be stopped, or may be continued if the patient is continuing to derive clinical benefit in the opinion of the investigator.

Patients will be assessed as per visit schedule in [Table 7-1](#).

Visit windows of \pm 1 calendar day will be applicable to scheduled study assessments during Cycle 1. Visit windows of \pm 3 days from scheduled study assessments will apply during and beyond Cycle 2. The only exception is imaging assessments, which have a \pm 7 day window at all scheduled time points.

7.1.3 Discontinuation of study treatment

A patient will be defined as on the study if they are continuing to have any study data collected, i.e. if the patient is being treated with LDK378, is in efficacy follow-up after discontinuing LDK378, or is in survival follow-up.

Patients may voluntarily withdraw from study treatment for any reason at any time. If a patient decides to discontinue from the study treatment, the investigator must make every effort (e.g., telephone, e-mail, letter) to determine the primary reason for this decision and record this information in the patient's chart and on the appropriate eCRF pages. They may be considered withdrawn if they state an intention to withdraw, fail to return for visits, or become lost to follow-up for any other reason.

The investigator should discontinue study treatment for a given patient if, he/she believes that continuation would be detrimental to the patient's well-being.

Study treatment must be discontinued under the following circumstances:

- Emergence of adverse events, as described in [Section 6.3](#).
- Laboratory abnormalities, as described in [Section 6.3](#).
- Pregnancy
- Deviations from the prescribed dose regimen, as described in [Section 6.1.1](#).

- Use of prohibited treatment, as described in [Appendix 1](#) for LDK378
- Any other protocol deviation that results in a significant risk to the patient's safety
- Study Terminated by Sponsor
- Patient/guardian decision
- Physician decision
- Lost to follow-up
- Death

Patients may permanently stop the study treatment for one of the following reasons:

- Progression of disease (radiological assessment by investigator)
- Technical Problems
- Protocol deviation

Patients who discontinue study treatment should NOT be considered withdrawn from the study. They should return for the assessments indicated in [Table 7-1](#). If they fail to return for unknown reasons, every effort (e.g., telephone, email, letter) should be made to contact them as specified in [Section 7.1.5.4](#).

Patients who become pregnant during the trial must be withdrawn ([Section 8.4](#)). Patients who become pregnant must cease all tumor assessments regardless of whether or not they developed Progressive Disease.

Patients who discontinue study treatment during the treatment phase should be scheduled for a visit as soon as possible and within 7 days after the last dose of study treatment, at which time all of the assessments listed for the EOT visit will be performed. If a patient withdraws from treatment at a study visit, EOT assessments do not need to be repeated. An End of Treatment Phase Disposition eCRF page should be completed, giving the date and reason for stopping LDK378 treatment.

At a minimum, all patients who discontinue study treatment, including those who refuse to return for a final visit, will be contacted for safety evaluations during the 30 days following the last dose of study treatment.

If patients refuse to return for these visits or are unable to do so, every effort should be made to contact them or a knowledgeable informant by telephone to determine the survival status.

Patients who discontinue study treatment should be considered withdrawn from the study after the final visit assessments are performed or when it is clear that the patient will not return for these assessments.

If a patient discontinues study treatment, but continues study assessments, (e.g. during post treatment follow up phase as detailed in [Table 7-1](#)), the patient remains on study until such time as he/she completes protocol criteria for ending study assessments. At that time, the reason for study completion should be recorded on the End of Post Treatment Phase Disposition (Study Phase Completion) eCRF page.

Patients who discontinue study treatment should enter the survival follow-up period or continue tumor assessments when appropriate. Tumor assessments will continue until

progression of disease (radiological as assessed by investigator), patient withdraws consent from tumor assessments, patient is lost to follow-up, death or study terminated by Sponsor.

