6.1.1 Dosing regimen

LDK378 will be administered orally once daily at a dose of 750 mg (five 150 mg capsules) on a continuous dosing schedule. The treatment period will start on Cycle 1 Day 1.

Each study site will be supplied with LDK378 by Novartis. LDK378 is supplied as 150 mg hard gelatin capsules as individual patient supply, packaged in bottles. Medication labels will comply with legal regulation and be printed in local language. The storage conditions for the study treatment will be described on the medication label. LDK378 will be dispensed by the pharmacist or designee at the investigator's institution.

LDK378 will be administered orally once daily at a dose of 750 mg (five 150 mg capsules) on a continuous dosing schedule. The investigator must instruct the patient to take the study drug exactly as prescribed.

The general dose and treatment schedule of the study treatments are listed in [Table 6-1](#).

- Patients should take LDK378 once daily at approximately the same time each day in the morning, afternoon, or evening.
- Patients should take LDK378 on an empty stomach (i.e. fast from food and drink, except water) at least 1 hour before or 2 hours after a light meal. Each dose of LDK378 should be taken with a glass of water and consumed over as short a time as possible (i.e. not slower than 1 capsule every 2 minutes).
- Patients should be instructed to swallow whole capsules and not to chew or open them.
- If vomiting occurs during the course of treatment, no re-dosing of the patient is allowed before the next scheduled dose.

- Patients should be instructed not to make up missed doses or partial doses (i.e. when the entire dose is not taken as instructed). A missed or partial dose will be defined as a case when the full dose is not taken within 8 hours after the approximate time of the usually daily dosing. That day's dose (or part remaining dose) should be omitted and the patient should continue treatment with the next scheduled dose on the following day.

Table 6-1 Dose and treatment schedule

Study treatments	Pharmaceutical form and route of administration	Dose	Frequency and/or Regimen
LDK378	Gelatin capsule for oral use	750 mg (5 x 150 mg / capsule)	Once daily (28 day / cycle)

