6.3 Dose modifications

6.3.1 Dose modification and dose delay

For patients who do not tolerate the protocol-specified dosing schedule, dose adjustments are permitted in order to allow the patients to continue the study treatment. Any changes in LDK378 must be recorded on the Dosage Administration Record eCRF.

General guidelines for dose modifications for toxicities other than those listed in [Table 6-3](#).

For grade 1 and tolerable grade 2 treatment-related toxicities, patients are encouraged to continue at the current dose of study treatment. For intolerable grade 2 treatment-related toxicities, dosing should be interrupted until resolution to grade 1 or lower followed by dose reduction to the next dose level. For grade 3 or grade 4 treatment-related toxicity that is not considered by the investigator to be life-threatening, patients should interrupt study treatment until resolution to grade 1 or lower; then study treatment may continue following a dose reduction to the next dose level, if in the opinion of the Investigator, the patient continues to experience clinical benefit and after discussion with the Sponsor. For any grade 3 or 4 treatment-related toxicity that is considered by the investigator to be life-threatening, permanently discontinue study treatment.

More detailed LDK378 modification guidelines are described in [Section 6.3.3](#) and [Table 6-3](#) selected toxicities.

All dose modifications, interruptions or discontinuations must be based on the worst preceding toxicity as graded by the NCI Clinical Toxicity Criteria (NCI-CTCAE) version 4.03. Patients whose treatment is interrupted or permanently discontinued due to an AE must be followed until resolution or stabilization of the event. Patients requiring interruptions greater than 28 consecutive days will be discontinued from study treatment. In certain cases, if the Investigator and the Sponsor conclude that a patient, who has experienced a treatment interruption greater than 28 consecutive days, could benefit from additional treatment, continuation may be allowed.

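### Section 7.1.3 makes any deviation from the Section 6.1.1 dose regimen a mandatory reason to stop treatment, sets no threshold, and conflicts with permissive wording elsewhere in the protocol

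*Protocol*

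**What the plan says.** Protocol Section 7.1.3 has two lists of reasons for ending treatment.

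The first is mandatory: "Study treatment must be discontinued under the following circumstances". Among its entries are:

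- adverse events and laboratory abnormalities, each referred to Section 6.3;
- "Deviations from the prescribed dose regimen, as described in" Section 6.1.1;
- "Any other protocol deviation that results in a significant risk" to the patient's safety.

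The second list gives reasons for which patients may permanently stop. It includes protocol deviation, without further words.

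Section 6.1.1 sets out how the drug is taken: 750 mg once daily, on an empty stomach, capsules swallowed whole. On vomiting it says "no re-dosing of the patient is allowed before the next scheduled dose". On missed or partial doses it says "Patients should be instructed not to make up missed doses or partial doses". That day's dose, or what is left of it, is dropped and "the patient should continue treatment with the next scheduled dose on the following day".

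The glossary defines discontinuation of study treatment as permanent.

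**The concern.** A mandatory and permanent stop needs a stated trigger. The adverse-event and laboratory entries have one, because Section 6.3 contains graded stopping rules. The dose-regimen entry points to Section 6.1.1, which contains administration instructions and no rule for stopping.

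What is at stake is patient care and consistent conduct across sites. A site that follows the words would take a patient off the drug for a single dosing error, even if the tumour were responding. These patients have already received alectinib, and the protocol's own rationale says that few other ALK-targeted options remain. Another site would keep a similar patient on treatment and would then be at odds with a written 'must'.

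**Working it through.** No arithmetic applies. The check sets the texts side by side.

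**Step 1: does the entry carry a limit of its own?** No. It states no count, size, duration or risk level. 'Deviations' is plural, but no number is given.

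**Step 2: does the cross-reference supply one?** No. Section 6.1.1 gives no condition under which treatment ends.

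**Step 3: does the safety qualifier in the same list reach it?** Not by its wording. The significant-risk condition is attached to a separate entry, for any *other* protocol deviation.

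**Step 4: which events are left to the entry once 6.1.1 and 6.3 have been applied?**

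| Event | What 6.1.1 or 6.3 says happens next | Left to the 7.1.3 entry? |
|---|---|---|
| Missed or partial dose, omitted | 6.1.1: carry on with the next scheduled dose | No |
| Interruption for a reason other than toxicity | 6.3.2: may resume at the same dose | No |
| Interruption or reduction for toxicity | 6.3.1 to 6.3.3 and Table 6-3 | No |
| Re-dose after vomiting | 6.1.1 forbids it; no consequence stated | Yes |
| Missed dose made up later | 6.1.1 says patients should be told not to; no consequence stated | Arguable |
| Dose taken with food, or capsule chewed or opened | 6.1.1 advises against it; no consequence stated | Arguable |

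The last two rows are less clear because 6.1.1 words those rules as 'should'. The vomiting rule is worded as a prohibition.

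**Step 5: is the entry consistent with the rest of the protocol?** No.

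- Section 7.1.3 itself makes protocol deviation an optional reason.
- Appendix 2, Section 15.1.30, lists protocol deviation and non-compliance with study treatment as reasons for which patients may discontinue.
- The lists of reasons for ending treatment in Sections 4.1.2, 6.1.3 and 7.1.2 do not mention dose deviations. This is weaker evidence than the first two, because those lists also leave out use of prohibited concomitant medication in general, which 7.1.3 likewise makes mandatory.

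**Step 6: can a site obtain an exception?** Section 12 bars sites from asking the sponsor to approve a deviation. Section 12.1 allows immediate action only where a patient's safety requires it. Neither prevents a site from asking what the entry means.

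**The case against.** The strongest case on the other side is that no sensible reader would treat the entry as an automatic trigger. The mandatory list also contains death, loss to follow-up and decisions by the patient or physician. These are reasons to record at disposition, not events that oblige a site to act. The word 'other' in the safety-risk entry suggests that the deviation entries before it were meant to share the same standard. Appendix 2 treats non-compliance as an optional reason. The SAP expects dosing to vary: Section 2.6 summarises the percentage of days dosed and of days at full dose, and Section 4.6 allows for dose changes above the planned dose. All of this points to a narrower intent.

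Much of that stands as evidence of intent, and many investigators would probably read the entry that way. It does not supply the missing limit. Appendix 2 is a general guideline and does not override 7.1.3, and the SAP describes how doses are reported, not when treatment stops. The more evidence there is that a narrower rule was meant, the clearer it is that the mandatory wording is at odds with the rest of the protocol.

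Two further points are fair. Compliance is assessed at each visit partly from what the patient or caregiver reports (Section 6.6.3.1), so some breaches will never be known. Whether a site that continued treatment would be recorded as deviating depends on the Study Specification Document, which is not among the documents reviewed.

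**Conclusion.** The point holds as a wording fault of minor severity. The protocol states a mandatory, permanent stop without a threshold and contradicts it elsewhere. Taken literally, a single re-dose after vomiting would end treatment. The conclusion rests on that literal reading. It needs no assumption about how often breaches occur.

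Four stronger readings are tempting, and the documents do not support them.

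- *Many patients would be affected.* A reader might infer this from the vomiting rate of 157/255 (61.6%) at 750 mg in Section 1.2.1.2.1. That is how often the no-re-dosing rule becomes relevant, not how often it is broken. No breach rate is given.
- *The rule is out of proportion to the interruption rule.* Section 6.3.1 says "Patients requiring interruptions greater than 28 consecutive days will be discontinued from study treatment", and adds that where the investigator and sponsor conclude that the patient "could benefit from additional treatment, continuation may be allowed". But a prohibited extra dose and a managed interruption are different kinds of event. Section 6.3.1 also requires permanent discontinuation for life-threatening grade 3 or 4 treatment-related toxicity, so its 28-day limit is not its only stop.
- *Any missed dose or unplanned interruption forces a stop.* Sections 6.1.1 and 6.3.2 say what to do in those cases, and treatment can continue.
- *ORR or the stated operating characteristics would be biased.* Without a breach rate nothing can be sized. The entry concerns treatment conduct, not the analysis.

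**What to change.** Reword the entry in the mandatory list of Section 7.1.3 so that it covers only dose-regimen deviations that pose a significant risk to patient safety and are not already handled by Section 6.1.1 or 6.3. All other regimen deviations then fall under protocol deviation in the permissive list of the same section, which needs no change.

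The cost is one line in a protocol amendment, which could go in with the next one. Sample size, endpoints and SAP are unaffected.

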4.1.3 Follow-up period

Safety follow-up

All patients will be followed for AEs and SAEs for at least 30 days following the last dose of study treatment at the end of treatment phase.

Post-treatment follow-up

All patients who discontinued treatment during the treatment phase for reasons other than death, lost to follow-up, pregnancy or PD (radiological as assessed by investigator) ([Section 7.1.3](#)) will continue tumor assessments thereafter until PD (radiological as assessed by investigator), or withdrawal of consent or death.

Survival follow-up

All patients who had PD as per investigator assessment and/or withdrew consent from further study assessments will subsequently be followed for survival information every 3 months until death, lost to follow-up or withdrawal of consent for survival follow-up.

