4.3 Definition of end of the study

There will be no interim analysis of efficacy. The primary analysis will occur once all patients have completed at least 6 cycles of treatment with LDK378 or have discontinued earlier. Following the primary analysis time point, the study will remain open. Patients still being followed on the study will continue as per the schedule of assessments.

The study will end once at least approximately 75% of patients have died or are lost to follow-up. The final analysis of study data will be conducted at the end of the study. All available data from all patients up to this cutoff date will be analyzed. These data will be summarized in the Clinical Study Report (CSR).

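### Protocol section 7.1.3 gives two opposite study statuses for patients who stop treatment; a site applying the withdrawal sentence could cut short follow-up for PFS, DOR and OS

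*Protocol*

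**What the plan says.** Protocol section 7.1.3 opens by defining a patient as on the study while any study data are still collected, including when the patient "is in efficacy follow-up after discontinuing LDK378, or is in survival follow-up". It then states: "Patients who discontinue study treatment should NOT be considered withdrawn from the study", and sends such patients to the assessments in Table 7-1.

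Later in the same section comes the opposite instruction: "Patients who discontinue study treatment should be considered withdrawn from the study after the final visit assessments are performed". The sentence goes on to cover patients who clearly will not return for those assessments. It makes no exception for patients in tumor or survival follow-up.

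The next two paragraphs turn back. For a patient who stops treatment but continues assessments, "the patient remains on study until such time as he/she completes protocol criteria for ending study assessments". And: "Patients who discontinue study treatment should enter the survival follow-up period or continue tumor assessments when appropriate".

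Elsewhere the follow-up plan is consistent:

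- Protocol section 4.1.3 says that patients who stop for reasons other than death, loss to follow-up, pregnancy or PD "will continue tumor assessments thereafter until PD (radiological as assessed by investigator), or withdrawal of consent or death". Section 7.1.5.2 repeats this with an 8-week interval.
- Protocol section 7.1.5.3 sets survival contact every 12 weeks.
- SAP section 2.5 tabulates patients entering post-treatment efficacy follow-up and survival follow-up after the end-of-treatment page.

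On study closure, Protocol section 4.3 says: "The study will end once at least approximately 75% of patients have died or are lost to follow-up". SAP section 4.1 ties the final analysis to at least 75% of patients having died.

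**The concern.** Study status decides whether a site keeps collecting data. Two sentences in one section give the same patients opposite statuses, and a site can follow only one of them.

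A site that treats the patient as withdrawn after the final visit has a written basis for closing the record there. In a patient who stopped without progression, scans would end. In any patient still alive, telephone contact for survival could end. DOR is a key secondary endpoint, and PFS and OS are other secondary endpoints. All three need data from after the last dose in at least some patients. Stopping treatment often reflects toxicity or decline, so censoring tied to it is plausibly related to prognosis, which Kaplan-Meier estimation assumes it is not.

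**Working it through.** The point is textual, so most of the check is a comparison of passages.

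**1. Same patients?** Yes. Both sentences have patients who discontinue study treatment as their subject, and neither is restricted by reason for stopping.

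**2. Which visit is the final visit?** Two paragraphs before the withdrawal sentence, section 7.1.3 says that all who stop, "including those who refuse to return for a final visit, will be contacted for safety evaluations during the 30 days" after the last dose. The paragraph before that describes the end-of-treatment visit within 7 days of the last dose. The glossary entry *Stop study participation* takes the later of the final evaluation visit and drug discontinuation, which points the same way. Reading the final visit as the end of all follow-up is possible, but nothing in the text says so.

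**3. Does the surrounding text resolve it?**

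| Text | Status after stopping treatment |
|---|---|
| 7.1.3, definition of on study | On study through efficacy and survival follow-up |
| 7.1.3, first status sentence | Not withdrawn |
| 7.1.3, later status sentence | Withdrawn after the final visit, or when return is not expected |
| 7.1.3, next two paragraphs | On study while assessments continue; enters survival follow-up or continues scans |
| 4.1.3, 7.1.5.2 | Scans continue if no PD |
| 7.1.5.3 | Survival contact continues |
| SAP 2.5 | Both follow-up phases expected; survival follow-up has its own eCRF question |

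The intent is clear, but the contradicting sentence remains an operative instruction.

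**4. What happens to each endpoint if a site applies it?**

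- *Stopped with documented PD:* the PFS event has occurred, as has the DOR event in a responder. Only OS is exposed.
- *Stopped without PD:* scans end. SAP Table 2-2 censors PFS and DOR at the last adequate assessment. A later death more than 18 weeks after that assessment (D2 = 8 × 2 + 2 weeks, SAP section 4.7.1) is also censored for PFS, even if it is recorded.
- *Survival contact ends:* OS is censored at the last contact date (Protocol section 10.5.2, SAP sections 2.8.1 and 4.3).
- *Died on treatment:* nothing is lost.
- *Primary ORR:* a response first seen close to the last dose might miss its confirming scan. By default, Appendix 2 (section 15.1.17) already leaves scans more than 30 days after the last dose out of best response, so the effect is likely small.

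**5. Can the number affected be derived?** No. The nearest figure is in Protocol section 1.2.1.2.1: 10.2% of phase I patients at 750 mg stopped because of adverse events. Applied to this trial, 0.102 × 20 = 2.04 patients. That counts one reason only. Section 7.1.3 also lists patient decision and physician decision, and section 6.1.3 adds new anticancer therapy. Exposure becomes loss only where a site applies the sentence, and the documents give no rate for that.

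**6. End-of-study trigger.** 75% of 20 is 0.75 × 20 = 15 deaths, and 20 − 15 = 5. Under the SAP's deaths-only wording, if more than 5 patients were closed alive with no later death recorded, 15 deaths could not be observed. The protocol's wording also counts patients lost to follow-up, but does not say whether patients labelled withdrawn under section 7.1.3 belong there. If they count, the trigger comes sooner; if not, later or never. The direction is not established.

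**7. The plan's own figures.** The probability of at least 6 responders in 20 reproduces: 58.36%, 75.46% and 87.44% at true ORRs of 30%, 35% and 40%, against the stated 58.4%, 75.5% and 87.4%. None of these changes with this point.

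**The case against.** The strongest reply is that no careful site would stop follow-up. The two paragraphs after the sentence say that patients remain on study and enter follow-up. Section 7.1.3 also asks for every effort to establish survival status in patients who refuse visits. Section 7.1.5.3 follows for survival even those who withdrew consent from further assessments, and only full withdrawal of consent (section 7.1.4) bars contact. The eCRF asks about survival follow-up separately, so a withdrawn label does not by itself end it. The affected endpoints are secondary and descriptive, and no hypothesis is tested.

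Most of this stands. It shows that the design is stated consistently and that the fault is one of wording. It also limits the OS consequence to sites that disregard several other provisions. It does not remove the contradiction: the withdrawal sentence carries no exception, and nothing says which sentence governs.

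A reader might go further and infer that the plan ends PFS and OS follow-up at the end-of-treatment visit, that OS in all 20 patients is compromised, or that about 2 of 20 measures the PFS loss. The documents do not support these readings. Continued follow-up is the evident intent. The figure of 20 is a ceiling that assumes every site follows one sentence against the rest and that nobody dies on treatment. The figure of 2 covers adverse-event stops only. Nor is the censoring argument general: it does not apply to PFS or DOR in patients who stopped for documented PD.

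**Conclusion.** The contradiction in Protocol section 7.1.3 is real and should be corrected. It is an internal inconsistency that invites uneven site conduct, not a flaw in the intended design. If the withdrawal sentence is applied, PFS and DOR are censored early in patients who stopped without PD, plausibly informatively, and OS is censored at last contact.

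The size cannot be stated from the documents. It depends on how many patients stop without PD, for any reason, and on how many sites act on the sentence. With 20 patients, a few inconsistently closed records could matter for the descriptive secondary estimates. The primary ORR is unlikely to move much. The conclusion assumes that the final visit is the end-of-treatment visit, which nearby usage and the glossary favor but do not state outright.

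**What to change.** In Protocol section 7.1.3, take one of two routes:

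- delete the sentence that treats discontinued patients as withdrawn after the final visit; or
- limit it to patients who have completed, or have refused, all tumor and survival follow-up.

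Under either route, deal with the clause on patients who will not return. State that missing the final visit does not end participation, and that such patients still enter survival follow-up unless they withdraw consent for it. Align the glossary entry *Stop study participation* with the section 7.1.3 definition of being on the study.

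Deletion leaves no gap. Section 7.1.3 still says when a patient leaves the study, and sections 7.1.4 and 7.1.5.4 cover withdrawal of consent and loss to follow-up. The cost is a few words of amended text and a memo to sites. No visit, procedure or analysis is added.
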